## 4 STUDY DESIGN

### 4.1 Study Overview

1) We will screen for eligible subjects using the computer algorithm on spirometry data abstracted from Apex monthly and by suggestion of the transplant pulmonologists. 2) Then, we will review CT scans to adjudicate a diagnosis of RCLAD. 3) Finally, our pharmacist will determine if tacrolimus dose is stable. After these 3 steps are completed subjects will be eligible for the study.

Subjects will be recruited at their transplant clinic visit or by phone if they previously consented to be contacted with new research study opportunities. We will seek to enroll ten subjects, who will receive pirfenidone for 52 weeks, titrated to 2403 mg/day (3 capsules, 3× daily) over a period of six weeks. Genentech has agreed to provide study drug free of cost.

TEAE will be recorded and graded according to the Common Terminology Criteria for Adverse Events (CTCAE) v3.0^21. Our study coordinator will contact subjects by phone every 2 weeks for the first 6 weeks to inquire about TEAE and then monthly. Subjects will be provided a phone number to report any additional TEAE. A Data Safety Monitoring Board will be convened.

As part of their routine post-transplant surveillance, subjects have monthly laboratory testing that includes tacrolimus blood concentration and liver function tests. Therefore, the manufacturer recommendations of monitoring liver function tests monthly for the first six months and then every 3 months while taking Pirfenidone, will be followed.

Subjects will continue their routine care with clinic visits, spirometry and CT as clinically indicated. In our clinical practice, subjects with RCLAD are expected to have a clinic visit and spirometry approximately every 3 months and a CT scan every 6 to 12 months.

If RCLAD subjects in the study undergo bronchoscopy for a clinical indication, bronchoalveolar lavage, biopsies, airway brushes and plasma specimens will be collected in the biorepository for future analysis of changes in pro-fibrotic mediators after initiation of pirfenidone. These specimens will be collected as part of the ongoing "Lung Transplantation: Improving outcomes through the development of a clinical database and biorepository" study number 13-10738. In the future, we plan to explore whether subjects with RCLAD have a greater rate of decline in telomere length in airway epithelial cells compared subjects without RCLAD.

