## 8 STATISTICAL METHODS AND CONSIDERATIONS

Prior to the analysis of the final study data, a detailed Statistical Analysis Plan (SAP) will be written describing all analyses that will be performed. The SAP will contain any modifications to the analysis plan described below.

**Interim analysis plans:** We will plan interim analyses of data quality and patient compliance on a quarterly basis to insure adequate study conduct. Modifications to the study conduct (e.g. changes to the outcome measures, or even cessation of the study if indicated by issues with performance or outcomes) will be considered at each of these analyses.

**Power:** This is a pilot study with the primary outcome of determining pirfenidone tolerability and its effect on tacrolimus dosing. Even with a small cohort, we hypothesize we will be powered to detect a significance difference in tacrolimus dosing. Based on the single report of tacrolimus dosing increase of 2.5 fold, and conservatively estimating a standardized effect size of 1 (doubling of tacrolimus dose and a standard deviation of the

change of 50%), a sample of 8 subjects would be required to detect a significant difference, assuming a two-sided  $\alpha$  of 0.05 and  $\beta$  of 0.20.

**Data analysis plan:** Since we will be comparing within subject changes, we will use paired t-test to compare the tacrolimus-on-pirfenidone to tacrolimus-off-pirfenidone ratio. For analyses involving repeated measures including change in FVC, fibrosis score, and telomere length, we will use mixed effects models including subject as a fixed effect. Slopes before and after the initiation of pirfenidone will be compared.

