**Discontinuation:**

Patients may temporarily suspend all study drugs for up to 28 consecutive days if they experience toxicity that is considered related to study treatment and that requires a study

treatment hold. Patients who miss > 28 consecutive days of scheduled study treatment because of drug-related adverse events will be discontinued from the study. Exceptions may be made after discussions with the investigators, approval by the Medical Monitor, and consistency with the regulations of the Institutional Review Board/Ethics Committee (IRB/EC).

Patients who miss 14 or more days of Pirfenidone should reinitiate treatment by undergoing the initial 4 week titration regimen up to the full maintenance dosage. For treatment interruption of less than 14 days, the dosage prior to the interruption can be resumed.

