## **DOSE MODIFICATIONS**

### **Dose-reduction Procedure for Adverse Event Management:**

If patients experience significant adverse reactions (i.e., gastrointestinal, photosensitivity reaction or rash), they will have the following temporary dose reduction: reduce dose to 267 mg three times daily (801 mg/day) for 14 days, followed by 534 mg three times daily (1602 mg/day) for another 14 days, prior to returning to the protocol dose of 801 mg three times daily (2403 mg/day). If adverse reactions do not resolve with reducing dose to 267 mg three times daily (801 mg/day) for 14 days, patients will discontinue pirfenidone for 14 days. Any return to protocol dose level after dose reduction must follow documentation of resolution of the adverse event and after discussion with the medical monitor.

If a patient exhibits 2-3 times the upper limit of normal (ULN) ALT and/or AST elevation without symptoms or hyperbilirubinemia after starting Pirfenidone therapy, he/she will discontinue Pirfenidone for 14 days and reinitiate treatment by undergoing the initial 4-week titration regimen up to the full maintenance dosage if tolerated and repeat liver chemistry tests are within normal limits. We will exclude other causes, monitor the patient closely, and repeat liver chemistry tests as clinically indicated.

If a patient exhibits >3 times ULN ALT and/or AST elevation he/she will permanently discontinue Pirfenidone and will not be re-challenged with it.

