## **WITHDRAWAL**

### **Discontinuation of Patients:**

The investigator will discontinue patients from the study drug or the study or both in the following circumstances:

- The patient, for any reason, requires treatment with another therapeutic agent that has been demonstrated to be effective for treatment of the study indication. In this case, discontinuation from the study occurs prior to introduction of the new agent.

- The investigator decides that the patient should be withdrawn from the study. If a serious adverse event or a clinically significant laboratory value is the basis for this decision, the investigator will discontinue the study therapy and take appropriate measures. The investigator must **immediately** notify the study sponsor or its designee.
- The patient or attending physician requests withdrawal of the patient from the study.
- The investigator or the study sponsor stops the study or stops the patient's participation in the study for medical, safety, regulatory, or other reasons consistent with applicable laws, regulations, and good clinical practice (GCP).
- The study therapies have shown unacceptable toxicity.
- The patient becomes pregnant or fails to use adequate birth control (for women with reproductive potential).
- The patient is noncompliant with study procedures.

When a subject withdraws before completing the study, the reason for withdrawal is to be documented in the CRF and in the source document.

Study agents assigned to the withdrawn subject may not be assigned to another subject. Subjects who withdraw will not be replaced.

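### Removal from the study, not only from drug, after a long toxicity hold leaves the post-initiation FVC and CT slopes resting mostly on subjects who tolerate pirfenidone

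*Combined protocol and SAP*

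**What the plan says.** Three places deal with stopping, and they do not line up.

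- Data and Safety Monitoring Plan, Discontinuation: "Patients who miss > 28 consecutive days of scheduled study treatment because of drug-related adverse events will be discontinued from the study". The next sentence softens this: "Exceptions may be made after discussions with the investigators, approval by the Medical Monitor" and consistency with IRB/EC regulations are required. Holds of up to 28 days do not trigger removal.
- Withdrawal, Discontinuation of Patients: "The investigator will discontinue patients from the study drug or the study or both in the following circumstances". The list that follows does not say which of the three outcomes goes with which circumstance. It ends with "Subjects who withdraw will not be replaced".
- Dose Modifications: for ALT or AST above 3 times ULN, "he/she will permanently discontinue Pirfenidone and will not be re-challenged with it". Study status is not given. If the event is judged drug-related, the subject would in time also meet the 28-day rule.

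On data collection, section 4.1 says "Subjects will continue their routine care with clinic visits, spirometry and CT as clinically indicated", and section 6 describes spirometry and CT as part of clinical care. No passage says these results are collected after a subject leaves the study. The extension in section 6 monitors subjects only while they remain on drug.

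On analysis, section 8 plans mixed effects models with subject as a fixed effect and says "Slopes before and after the initiation of pirfenidone will be compared". It names no analysis set, no estimand and no handling of data after discontinuation.

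**The concern.** There is no control arm, so the before/after slope comparison is the plan's main efficacy signal. Section 2 says early evidence of slower FVC decline and radiographic progression is to inform a multicenter randomised trial. If subjects who cannot tolerate the drug leave the study, the slope after initiation is estimated largely on a selected group, while the slope before initiation can include everyone. If tolerance and rate of decline are related, the comparison can show a slowing, or hide one, merely because different people are being measured. The readings needed to check this would probably exist in the chart. A statistical analysis plan written later cannot use them unless the protocol provides for collecting them.

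**Working it through.** The plan gives no figure for the slopes, so the check starts from its own expectation of discontinuations.

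**1. How many leave.** The Stopping Rules section quotes 14.6% (IPF trials), 25% (its own upper limit) and 28.7% (post-authorisation observational study). Section 4.1 states "We will seek to enroll ten subjects".

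- Expected number: 10 × 0.146 = 1.46; 10 × 0.25 = 2.5; 10 × 0.287 = 2.87. The last two round to the plan's figure of up to 3.
- Binomial chance of at least one: 0.79, 0.94 and 0.97.
- Binomial chance of at least three: 0.17, 0.47 and 0.58.

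Not every such stop need fall under the 28-day rule, which covers drug-related events only.

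**2. What is left for a leaver.** The observational study's median time to discontinuation is 99.5 days: 99.5/7 = week 14.2. Removal 28 days later is (99.5 + 28)/7 = week 18.2. The section 6 schedule marks FVC at weeks 8, 20, 32, 44 and 52 and CT at week 24. A leaver at the median therefore has 1 of 5 FVCs and 0 of 1 CT.

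With three such leavers, and ignoring deaths:

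- FVC: 7 × 5 + 3 × 1 = 38 readings instead of 50, of which 3/38 = 8% come from leavers.
- CT: 7 instead of 10, none from leavers.

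**3. What this could do to a common slope.** Assumptions not in the documents: an FVC reading at the start of drug, complete FVC in all who stay, one common slope, no drug effect, and leavers declining 10 percentage points/year faster. The reference value is the equal-weight mean slope of all ten.

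A subject's information on the slope is the sum of squared deviations of visit times, in years:

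- Full schedule, weeks 0, 8, 20, 32, 44, 52 (mean 26): (676 + 324 + 36 + 36 + 324 + 676)/52² = 2072/2704 = 0.766.
- Weeks 0 and 8 only: (16 + 16)/2704 = 0.0118.
- Weeks 0, 8, 20, 32 (mean 15): (225 + 49 + 25 + 289)/2704 = 0.2175.

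For L leavers with information S each, their weight is w = L·S / (L·S + (10 − L) × 0.766), and the bias is (L/10 − w) × 10.

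| Leavers | Last FVC | w | Bias (points/year too shallow) |
|---|---|---|---|
| 1 | week 8 | 0.0017 | 1.0 |
| 2 | week 8 | 0.0038 | 2.0 |
| 3 | week 8 | 0.0066 | 2.9 |
| 3 | week 32 | 0.108 | 1.9 |

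The bias is proportional to the assumed 10-point gap. It is zero if the gap is zero and reverses sign if leavers decline more slowly.

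**4. Dependence on the model.** The table concerns the slope after initiation alone. For the full before/after comparison, take three leavers at week 8 and the same 10-point gap, and add assumed quarterly pre-drug FVCs.

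- Subject fixed effects, common slopes before and after, 2 to 4 pre-drug readings: apparent slowing of about 4.0 to 4.6 points/year with no drug effect. It is exactly 0 if all ten are followed to week 52.
- Random slopes (simulated): about 1.3 points/year.
- A separate slope change for each subject (simulated): indistinguishable from 0.

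Section 8 does not say which of these is meant.

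**The case against.** A reader might infer that the slopes describe only tolerators, or that the plan removes every intolerant subject. The documents support neither. Readings before removal are not excluded from the model, holds of 28 days or less stay in, exceptions can be approved, and the Withdrawal section already allows a subject to stop drug without leaving the study.

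A reader might also take 2.9 points/year as the expected bias. It is not. It puts three leavers at the median stopping time, although about half would stop later, and uses a gap that the documents nowhere support. The plan speaks of up to 3, and 14.6% implies 1.46 of 10. The calculation also gives every remaining subject complete FVC, although the synopsis says about 60% of RCLAD patients die within a year.

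Finally, an on-treatment slope is a legitimate target for a pilot, these are secondary outcomes, and the primary tolerability count does not depend on this rule.

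All of this stands, and it limits the size and certainty of the point. It does not answer the gap itself: the one explicit rule for a long toxicity hold is removal from the study, no follow-up is provided afterwards, and the plan does not say whether the slope is meant as on-treatment or regardless of adherence.

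**Conclusion.** The concern holds in limited form. The stopping passages are unreconciled and follow-up after removal is unspecified, so the post-initiation slopes would rest mostly (FVC) or almost entirely (CT) on subjects who tolerate the drug. The loss of readings follows from the plan's own numbers, given a stop at the cited median. The bias does not, because it requires that decline differ between leavers and others. With a 10-point gap and a common slope, the post-initiation slope is about 1.0 to 2.9 points/year too shallow for 1 to 3 leavers. It shrinks with later exits and subject-specific slopes, and is nil if decline is unrelated to tolerance. This should be corrected because the slopes are meant to inform the randomised trial, but it does not threaten the primary outcome.

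**What to change.** 1. Reconcile the Discontinuation, Dose Modifications and Withdrawal passages so that each states study status separately from drug status, and stopping drug does not by itself end data collection. This needs no change to, or choice of, any drug-stopping rule.
2. State that routine-care FVC, CT, tacrolimus level and vital status are abstracted to week 56 regardless of drug status, unless consent is withdrawn.
3. In section 8, define the slope after initiation on all subjects regardless of adherence, with an on-treatment analysis as supportive. State whether slopes are common or subject-specific.

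The cost is wording plus chart abstraction for about 1 to 3 subjects. The downside is that off-drug time dilutes the on-drug estimate. In a simulation with an assumed slope of −8 points/year on drug and −20 off drug, and 3 of 10 stopping near week 14, the mean slope was −8.0 with data truncated at removal and −10.8 with full follow-up. With equal slopes on and off drug, both were about −8. The two analyses answer different questions, so both should be shown.

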## **DOSE MODIFICATIONS**

### **Dose-reduction Procedure for Adverse Event Management:**

If patients experience significant adverse reactions (i.e., gastrointestinal, photosensitivity reaction or rash), they will have the following temporary dose reduction: reduce dose to 267 mg three times daily (801 mg/day) for 14 days, followed by 534 mg three times daily (1602 mg/day) for another 14 days, prior to returning to the protocol dose of 801 mg three times daily (2403 mg/day). If adverse reactions do not resolve with reducing dose to 267 mg three times daily (801 mg/day) for 14 days, patients will discontinue pirfenidone for 14 days. Any return to protocol dose level after dose reduction must follow documentation of resolution of the adverse event and after discussion with the medical monitor.

If a patient exhibits 2-3 times the upper limit of normal (ULN) ALT and/or AST elevation without symptoms or hyperbilirubinemia after starting Pirfenidone therapy, he/she will discontinue Pirfenidone for 14 days and reinitiate treatment by undergoing the initial 4-week titration regimen up to the full maintenance dosage if tolerated and repeat liver chemistry tests are within normal limits. We will exclude other causes, monitor the patient closely, and repeat liver chemistry tests as clinically indicated.

If a patient exhibits >3 times ULN ALT and/or AST elevation he/she will permanently discontinue Pirfenidone and will not be re-challenged with it.

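### ALT/AST at 2-3 times ULN with raised bilirubin has no mandatory action in the main 56 weeks, while the same elevation without it requires a 14-day hold

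*Combined protocol and SAP*

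**What the plan says.** The liver rules are in the Data and Safety Monitoring Plan, under Dose Modifications, Dose-reduction Procedure for Adverse Event Management.

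- **Hold.** The trigger is: "If a patient exhibits 2-3 times the upper limit of normal (ULN) ALT and/or AST elevation without symptoms or hyperbilirubinemia after starting Pirfenidone therapy". The action is 14 days off drug and then the 4-week titration, "up to the full maintenance dosage if tolerated and repeat liver chemistry tests are within normal limits". Excluding other causes, close monitoring and repeat liver tests are set out in the same paragraph.
- **Permanent stop.** "If a patient exhibits >3 times ULN ALT and/or AST elevation he/she will permanently discontinue Pirfenidone and will not be re-challenged with it".
- **Adverse-reaction rule.** This comes before the liver rules: "If patients experience significant adverse reactions (i.e., gastrointestinal, photosensitivity reaction or rash), they will have the following temporary dose reduction". It starts at 801 mg/day for 14 days. Only if the reaction does not resolve does it say that "patients will discontinue pirfenidone for 14 days". Going back up is conditional: "Any return to protocol dose level after dose reduction must follow documentation of resolution of the adverse event and after discussion with the medical monitor".

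The Discontinuation paragraph just before this adds a general hold, "Patients may temporarily suspend all study drugs for up to 28 consecutive days if they experience toxicity", and a limit, "Patients who miss > 28 consecutive days of scheduled study treatment because of drug-related adverse events will be discontinued from the study".

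**The concern.** The qualifier on the hold reads most naturally as requiring that both symptoms and hyperbilirubinemia be absent. A subject with the same enzyme elevation and a rising bilirubin is then outside the hold and still below the level for permanent discontinuation. That is the more worrying presentation, yet the written rule requires something definite only for the milder one.

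This is a patient-safety matter. The protocol's own section on events of special interest acknowledges postmarketing liver injury with this drug, including deaths. It also touches the primary outcome, discontinuation for a treatment-emergent adverse event. If one subject in this cell is stopped and another continues because two clinicians judged differently, the outcome partly reflects the absence of a rule.

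**Working it through.** The plan states no figure on this point, so the check is to map each presentation to the action the text requires in the main 56 weeks.

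| ALT/AST | No symptoms, bilirubin normal | Hyperbilirubinemia | Symptoms suggestive of liver injury |
|---|---|---|---|
| 2-3 times ULN | 14-day hold; restart if tests normal | No mandatory action | No mandatory action, if this is what symptoms means |
| Above 3 times ULN | Permanent stop | Permanent stop | Permanent stop |

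Does any other text fill the two empty cells?

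1. **Events of special interest (Section 11.3).** Both Hy's law definitions need ALT or AST above 3 times ULN. They govern reporting, not dosing.
2. **Discontinuation.** The general hold is permissive and names no liver threshold.
3. **Withdrawal.** The investigator must stop drug for unacceptable toxicity, but that is undefined. The clause on a clinically significant laboratory value applies once the investigator has decided to withdraw the subject. Both depend on judgement.
4. **Liver test tracking (Section 6).** It sets a monitoring schedule with no action attached.
5. **Entry criteria.** Bilirubin above ULN excludes at entry (Section 5.3). The Synopsis exempts predominantly unconjugated hyperbilirubinemia such as Gilbert's disease; Section 5.3 does not. A subject admitted under that exemption who reached 2-3 times ULN would, read literally, be outside the hold because of baseline bilirubin alone.
6. **Extension (Section 6, Protocol Amendment).** Subjects must go on meeting the entry criteria. That brings in the bilirubin limit after week 56. It does not help a symptomatic subject at 2-3 times ULN with normal bilirubin, because the enzyme criterion excludes only above 3 times ULN. The symptom cell therefore stays empty in the extension.

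The bilirubin cell is thus empty in the main 56 weeks, and the symptom cell, on the hepatic reading, is empty throughout.

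Two pieces of arithmetic bear on the cost of a fix. One subject of 10 is 1/10 = 10 percentage points of the discontinuation outcome. A 14-day hold leaves 28 - 14 = 14 days before the missed-treatment limit.

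**The case against.** The strongest reply is that the qualifier was meant to keep automatic hold-and-restart for mild cases and leave worse cases to clinical decision. The protocol nowhere tells anyone to continue drug. Investigators review each patient at monthly meetings, the Medical Monitor reviews quarterly, and the Withdrawal section lets an investigator stop drug for a laboratory value. In a single-site, open-label study of 10 subjects, some reliance on judgement is reasonable, and a careful clinician would probably stop.

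That is a plausible account of the intent, and it limits the weight of the point. It does not remove it, because no action for the worse cases was written down.

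Three stronger readings are tempting and are not supported:

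- A reader might infer that potential Hy's law cases can stay on drug. They cannot: both patterns lie above 3 times ULN, where the stop is mandatory. Nor does the protocol tie the fatal liver injuries it mentions to the 2-3 times band.
- A reader might infer that gastrointestinal symptoms move a subject from the hold to the weaker dose reduction. That needs two assumptions: that such complaints count as symptoms in the liver rule, and that the adverse-reaction rule then displaces it. The text says neither. Return to full dose on that route also needs resolution of the adverse event, and Section 11.2.2 counts laboratory findings as adverse events, so the enzyme elevation could be included.
- A reader might infer that every symptomatic subject loses the hold. Read that broadly, the qualifier could exclude RCLAD patients with ordinary respiratory symptoms. The hepatic reading is more sensible, but the term is undefined.

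**Conclusion.** The concern holds for bilirubin. In the main 56 weeks, ALT/AST at 2-3 times ULN with new or worsened hyperbilirubinemia has no mandatory action, whereas the same elevation without symptoms or hyperbilirubinemia requires 14 days off drug. This rests on the natural reading of the qualifier and on the other sections being permissive, judgement-based or limited to entry and the extension.

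The symptom limb holds with less certainty. It depends on symptoms meaning those suggestive of liver injury; if so, it is open in the extension as well.

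The gap is narrow, and the documents give no frequency for these presentations, so the number of subjects affected cannot be estimated. It still merits an amendment, because the missing case is the higher-risk one and the repair is small.

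**What to change.** Amend the liver paragraph under Dose Modifications as follows:

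- Any ALT and/or AST at 2-3 times ULN triggers at least the 14-day hold and exclusion of other causes.
- With new or worsened hyperbilirubinemia, or symptoms suggestive of liver injury, pirfenidone stops at once. It is not restarted unless another cause is documented, liver tests are normal (or bilirubin is back at baseline) and the medical monitor agrees. Permanent discontinuation under Withdrawal remains available, so the new text does not entitle the higher-risk case to rechallenge.
- For any subject admitted under the Synopsis exemption for unconjugated hyperbilirubinemia, worsening is judged against baseline. Reconcile that exemption with Section 5.3, which omits it.
- Define symptoms as those suggestive of liver injury.
- State that the liver rule takes precedence over the gastrointestinal, photosensitivity and rash dose reduction.

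This is a short amendment with no new tests, since bilirubin and symptoms already define the hold. The cost is a few more holds and possibly one more discontinuation for a treatment-emergent event. That one subject would be 10 percentage points of the primary outcome and would count toward the rule that stops enrolment after more than 3 such discontinuations. A hold alone is not a discontinuation: 14 days remain before the 28-day limit, and the protocol allows exceptions to that limit.

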### 5.3 Exclusion Criteria

Patients with RCLAD will be excluded if they are, in the judgment of the investigator, unlikely to tolerate pirfenidone. Other exclusion criteria will include:

1. FVC decline related to non-RCLAD causes (e.g. pulmonary edema, pleural effusion, etc).
2. Patients with any severe comorbidity complicating RCLAD which might determine their prognosis and functional level (e.g. active malignant disease) within the last 12 months.
3. Patients who have resumed smoking after transplantation.
4. Renal insufficiency (creatinine clearance < 30 ml/min calculated by the CKD-Epi formula).
5. Total bilirubin above the upper limit of the normal range (ULN)
6. Aspartate or alanine aminotransferase (AST or ALT) > 3 times the ULN.
7. Known allergy of hypersensitivity to Pirfenidone
8. Ongoing use or expected use of any of the following therapies:
  - Strong inhibitors of CYP1A2 (e.g. fluvoxamine or enoxacin).
  - Moderate inhibitors of CYP1A2 (e. g. mexiletine, thiabendazole, or phenylpropanolamine). Ciprofloxacin will be allowed only at doses equal or less than 500 mg BID.
9. Inability to provide informed consent.

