#### 11.3.2.3 c. *Preexisting Medical Conditions*

A preexisting medical condition is one that is present at the start of the study. Such conditions should be reported as medical and surgical history. A preexisting medical condition should be re-assessed throughout the trial and reported as an AE or SAE only if the frequency, severity, or character of the condition worsens during the study. When reporting such events, it is important to convey the concept that the preexisting condition has changed by including applicable descriptors (e.g., “more frequent headaches”).

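### A subject who enters with stable AST/ALT of 2-3 times ULN must be held at the first on-drug test and has no stated restart path, and the plan does not say how such a case is counted

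*Combined protocol and SAP*

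**What the plan says.** **Entry.** Section 5.3, item 6, excludes "Aspartate or alanine aminotransferase (AST or ALT) > 3 times the ULN", and the synopsis agrees. Any value up to and including 3 times ULN is eligible.

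**Hold.** The dose-reduction procedure under Dose Modifications begins: "If a patient exhibits 2-3 times the upper limit of normal (ULN) ALT and/or AST elevation without symptoms or hyperbilirubinemia after starting Pirfenidone therapy". The consequence is: "he/she will discontinue Pirfenidone for 14 days and reinitiate treatment by undergoing the initial 4-week titration regimen". Restart is qualified by "if tolerated and repeat liver chemistry tests are within normal limits". The trigger and the restart condition are both absolute levels, and neither refers to the subject's baseline.

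**Permanent stop.** This too is an absolute level: "If a patient exhibits >3 times ULN ALT and/or AST elevation he/she will permanently discontinue Pirfenidone".

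**Long interruptions.** The Discontinuation paragraph says: "Patients who miss > 28 consecutive days of scheduled study treatment because of drug-related adverse events will be discontinued from the study". The next sentence softens this: "Exceptions may be made after discussions with the investigators, approval by the Medical Monitor".

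**What counts as an AE.** Under Section 11.3.2.3 a pre-existing condition is "reported as an AE or SAE only if the frequency, severity, or character of the condition worsens during the study". Section 11.1.2 takes the same line. Section 11.2.4 assigns no causal relationship to pirfenidone where there is evidence of another origin, and gives a pre-existing condition as an example.

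**Where the count is used.** The primary tolerability outcome in the synopsis is the number of subjects stopping pirfenidone because of a TEAE. Under Stopping Rules, enrolment of new subjects ends once more than 3 have stopped early because of an AE. Withdrawn subjects are not replaced.

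**The concern.** Every value from 2 to 3 times ULN is both acceptable at entry and a reason to interrupt treatment afterwards. For a subject who starts in that band and stays there, the hold reflects no change on drug. The restart condition asks for a result that the subject did not have at enrolment.

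With ten subjects and no replacement, one such case is 1/10 of the primary outcome. The AE definitions point towards leaving it out of the tolerability counts. However, the hold rule and the 28-day rule do not refer to those definitions, so the classification depends on how the site reads the hold.

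**Working it through.** **1. Overlap of the rules.** Eligible: AST/ALT up to 3 times ULN. Hold: 2-3 times ULN after starting drug. The overlap is the whole 2-3 band. Subjects entering below 2 times ULN with no change are not affected. The hold rule applies to elevations without symptoms or hyperbilirubinemia, and a subject with no symptoms and normal bilirubin fits that description.

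**2. Worked path at a constant 2.5 times ULN**
- Entry: eligible.
- Week 4, the first liver test in the Section 6 schedule: 2.5 lies in the 2-3 band, so the 14-day hold starts.
- Week 6: the 14 days end. The tests are not normal, so the restart condition is not met.
- Week 8, the next scheduled test: still 2.5, and day 28 of the hold. The 28-day limit is passed the next day.
- Change from baseline throughout: 2.5 - 2.5 = 0.

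Extra tests may be done as clinically indicated, but at a constant value they would not alter the path.

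**3. Is this a drug-related AE?** Sections 11.1.2 and 11.3.2.3 require a pre-existing condition to worsen, and this one has not. Under Section 11.2.4 a pre-existing cause leads to a causality answer of No. The 28-day rule covers only days missed because of drug-related AEs, so on a strict reading it does not apply, and neither do the primary outcome or the stopping count. The subject is still off drug with no stated route back.

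The liver criteria among the AEs of special interest are limited to treatment-emergent elevations. The hold rule has no such limit.

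**4. Size if such cases were counted.** The plan states no figure for this point. The inputs are n = 10, the 14.6% reference rate and a limit of more than 3, all from Stopping Rules. Let k be the number of subjects who stop only by this route and are counted as AE discontinuations. The other 10 - k stop independently at rate p:

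P(at least 4 of 10) = P(X >= 4 - k), X ~ Binomial(10 - k, p)

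At p = 0.146:
- k = 0: 1 - (0.2063 + 0.3528 + 0.2714 + 0.1237) = 0.0458
- k = 1: 1 - (0.2416 + 0.3718 + 0.2542) = 0.1324
- k = 2: 1 - (0.2829 + 0.3869) = 0.330

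At 28.7%, the observational-study rate that the plan also cites, the same formula gives 0.316, 0.502 and 0.718.

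The range k = 0 to 2 is an assumption, because the documents do not say how many candidates have values of 2-3 times ULN. For a given p and k, each figure is an upper bound on the chance that the rule alters the trial. A fourth discontinuation after the tenth enrolment has nothing left to stop.

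**The case against.** A reader might infer that the rules force an unchanged subject out of the study and so bias the primary outcome and the stopping count. The documents do not support that. Read together, Sections 11.1.2, 11.2.4 and 11.3.2.3 make an unchanged value neither an AE nor drug-related. The 28-day rule is confined to drug-related AEs and allows exceptions with Medical Monitor approval. The hold rule also commits the investigators to exclude other causes, which should bring a pre-existing elevation to light. Entry in this band is not automatic either, because anyone judged unlikely to tolerate pirfenidone is excluded.

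A reader might also infer that the entry and hold limits must be equal. They need not be, since they serve different purposes. The gap is narrower: the hold and restart rule makes no provision for an abnormal baseline.

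These objections remove the claim of forced study discontinuation and of demonstrated bias. They leave two things standing. The hold and the restart condition do not depend on the search for other causes, so the subject remains off drug whatever it finds. Case-by-case exceptions also do not define how a case is counted. The restart wording could be read as governing only the return to full dose. On that reading the subject still could not reach the protocol dose, and each later value in the band would meet the hold trigger again.

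**Conclusion.** The point holds as a gap in the rules for subjects with an abnormal baseline. As written, a subject eligible at a stable 2-3 times ULN is held at the first on-drug test and has no stated restart path. The AE and causality definitions imply that this should not count in the primary outcome or the stopping rule, but the hold and 28-day rules do not say so. A site that treated the hold as drug toxicity would count it.

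The rise from 4.6% to 13.2% or 33.0% at the 14.6% rate shows how sensitive a ten-subject count would be to one or two misclassified cases. It is not a forecast. It assumes that those cases occur, that they are counted, and that enrolment is still open when the fourth discontinuation arises. The number of subjects affected is unknown and may be zero.

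**What to change.** 1. Reconcile the entry criterion (synopsis and Section 5.3) with the hold and restart rule under Dose Modifications and the 28-day rule under Discontinuation, for subjects whose baseline is already abnormal. The thresholds are a clinical choice for the investigators.
2. State that a liver-test hold or discontinuation counts in the primary outcome and the stopping rule only if it is an AE under the worsening criterion of Section 11.3.2.3, with causality assessed under Sections 11.2.2 to 11.2.4. A mechanical test of any rise from the last value would be a poor substitute: it has no margin for measurement noise and would displace the causality assessment.
3. Record a pre-pirfenidone AST/ALT value and list it for every liver-test discontinuation. Exclusion item 6 implies that a value exists, but its timing is not stated and the Section 6schedule shows no baseline column.

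The cost is small: added wording and one recorded value per subject. Some judgement on what counts as worsening will remain, because patients use their own chosen laboratories.
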